- average minutes of exercise per day conducted with the technology as an objective measure for activity participation
- acceptance of technology, based on the Technology Acceptance Model / TAM as in [11] and [33] provided to patients at the end of the study (see [Annex B](#)).

All previous measures will be evaluated in general and for 6 different age-gender groups (male and female below 55, between 55 and 70, above 70).

As secondary outcome measures we will assess objective scales and scores typical for stroke rehabilitation:

- the Barthel index (see [10], [19], [6], [8])
- the Modified Rankin Score (see [19], [30], [7], [8])
- 

These scores will be compared with standard values and the goal is to show equivalency or improvement from those standard values after the treatment with WeReha.

In addition, we want to demonstrate the logistical and economic benefits of the deployed solution. Dedicated figures (a nurse or physiotherapist hired to run the Clinical Trial research study as explained in the Methodology section) will objectively measure the time taken to training patients and caregivers before leaving the trial site with the device and the number of times patients contact the sponsor for technical assistance.

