#### **Secondary Outcome Measures:**

- Barthel index and Modified Rankin Score: change from baseline (measured when receiving the device) at the end of the rehabilitation treatment (when returning the device)
- Time dedicated by the specialised personnel to each patient for training to learn the WeReha device before leaving the trial site (measured in minutes/patient)
- Number of calls per week for clinical and technical assistance specific for the WeReha device, registered on a paper or software spreadsheet by the sponsor

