#### Inclusion criteria:

- Ages Eligible for Study: Over the age of 18
- Sexes Eligible for Study: All
- First-time ischemic or haemorrhagic stroke, as documented by a CT or MRI
- Patients able to sit for at least ten minutes and to look after own affairs without assistance i.e. a Modified Rankin Scale (MRS)≤ 2
- Montreal Cognitive Assessment (MoCA) ≥12
- Ability and willingness to participate in the study
- Complete a signed consent form

Exclusion criteria:

- Significant medical conditions that affected function prior to the stroke and would limit normal stroke rehabilitation (e.g. musculoskeletal condition affecting arm function or cardiac condition limiting basic activities of daily living).
- Bilateral weakness of upper extremities
- Unavailability of a caregiver
- Participation in another clinical trial involving rehabilitation (recreational therapy, occupational therapy, physiotherapy) or an investigational drug.

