## Data Management and Statistical Analysis

As the primary outcomes of the study are designed to evaluate the impact and acceptance of a new rehabilitative technology for stroke patients, a statistical analysis on the primary outcomes will not be conducted. On the other hand, the study clearly aims to evaluate the number of patients, meeting the inclusion/exclusion criteria that are willing to use this technology and the time they will be using the devices at home. It has also to be noted that this study is part of a research project (Magic-PCP, [5]) where 3 companies will provide their solutions to 1 hospital in Italy and sites in NI, i.e. each company will run a similar trial with identical numbers on different sites. The request and the funding to provide 75 devices on each country and aim at performing a validation on maximum 2 patients per device is a clear requirement of the project. We have then defined the primary and secondary outcomes that we consider crucial for evaluating our proposed technology.

The primary outcome will be evaluated in an anonymised form and considered good if planned KPIs are met or exceeded. Secondary outcomes will be evaluated using an unpaired test to compare pre and post intervention measured values, whereas the Chi-square test will be used to detect the significance of outlier proportions, p values smaller than 0.05 will be considered statistically significant. All calculations will be performed using the Matlab software tool (The Mathworks Inc., Natick, MA, USA). We are also interested in evaluating possible correlations among results for the different groups of patients under examination (male and female <55 years old, 55-70, more than 70) to be better prepared for a future clinical investigation of our device.

All details related to the Data Management are provided in Annex A - Technical Data Management of the present document.

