## Anticipated Results of the Study

As stated, this trial is part of the Magic-PCP project [5], and the results of the study aim to demonstrate the impact of the usage of technology for stroke patients and community on a large scale. The project anticipates that devices will be accepted by patients and integrated in their home treatment routine, that they will use it regularly and with the expectation that it improves motivation and as a consequence their quality of life and motor functions.

Results will be collated by the buyers group also with other ongoing studies within the umbrella of the Magic PCP project and compared eventually with existing studies that we referred to.

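### The goal of showing equivalency or improvement against standard values for Barthel and Rankin has no standard value, margin or test, and the planned pre/post comparison cannot support it

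*Combined protocol and SAP*

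**What the plan says.** Three sections bear on the Barthel and Rankin outcomes.

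- **Goal** (Study goals and objectives): "These scores will be compared with standard values and the goal is to show equivalency or improvement from those standard values". No value, population or source is identified as the standard. Some references are cited beside each scale, but none is named as supplying it.
- **Outcome** (Secondary Outcome Measures): "Barthel index and Modified Rankin Score: change from baseline (measured when receiving the device) at the end of the rehabilitation treatment". The reference point here is the patient's own start score.
- **Analysis** (Data Management and Statistical Analysis): "Secondary outcomes will be evaluated using an unpaired test to compare pre and post intervention measured values", with "p values smaller than 0.05 will be considered statistically significant". The same section adds that "the Chi-square test will be used to detect the significance of outlier proportions", without defining these outliers, and expresses interest in correlations across age and sex groups.

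Anticipated Results of the Study adds that results will be collated with the sister studies and "compared eventually with existing studies that we referred to", with no method or reference figure. Study Design restricts secondary outcomes to active patients.

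**The concern.** The goal and the analysis have different comparators. The goal refers to an external standard, and the analysis refers to the patient's own baseline. The goal also includes equivalency, while the only inferential output for these scores is a p-value for a difference.

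If the plan is followed exactly, the trial ends with a p-value for change and a stated aim that this p-value does not address. The report must then either leave the secondary goal unanswered or reach for a conclusion that the analysis does not license. The easiest one to reach for is that no significant change means equivalency. The plan contains nothing to prevent that.

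**Working it through.** **There is no figure to reproduce.** The documents give no sample-size calculation, power, SD, margin or standard value for either scale.

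**Step 1. What each possible result would show.**

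- *Significant improvement from baseline.* This shows that scores rose in these patients. The Project summary says that WeReha is used in addition to traditional treatment and that subacute patients are enrolled, so some rise is plausible without the device. Whether the rise or the end score reaches a standard value is not examined.
- *Significant decline from baseline.* Scores could still lie above or below a standard value. The test does not say.
- *Non-significant change.* This says only that a change was not detected. It is not evidence of similarity to baseline unless the confidence interval is narrow against a stated margin. It is no evidence at all about a standard value.

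The Chi-square test and the group correlations do not test equivalency either. The later comparison with existing studies has no method. The gap therefore exists at any sample size.

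**Step 2. How weak a non-significant p would be, even for change from baseline.**

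Inputs:

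- n = 40: minimum number of active patients (Primary Outcome Measures).
- n = 75: one patient per device.
- n = 150: 75 devices × 2 patients (Data Management and Statistical Analysis). This is an enrolment ceiling, so it is an upper bound on active patients.
- Test level 5%, taken as two-sided; the documents do not state sidedness.
- True decline of 0.2 or 0.3 SD of the within-patient change: an assumption.
- Paired t-test: an assumption that favours the plan.

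Method: the t statistic is noncentral t with n − 1 degrees of freedom and noncentrality d√n. The probability of non-significance is the probability that |t| stays below the critical value. For n = 40 and d = 0.3, the noncentrality is 0.3 × √40 = 1.897, the critical value is 2.023, power is 0.457, and the probability of non-significance is 0.543.

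| n | Decline 0.2 SD: P(non-significant) | Decline 0.3 SD: P(non-significant) | 95% CI half-width, t/√n |
|---|---|---|---|
| 40 | 77% | 54% | 2.023/√40 = 0.32 SD |
| 75 | 60% | 27% | 1.993/√75 = 0.23 SD |
| 150 | 32% | 5% | 1.976/√150 = 0.16 SD |

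The unpaired test named in the plan would do worse for these effects at n = 40. With an assumed pre/post correlation of 0.5, the SD of change equals the SD of a single score, so the scales match. For a 0.3 SD decline the unpaired statistic has mean 0.3/√(2/40) = 1.342 and SD √(1 − 0.5) = 0.707. The probability of non-significance is then about Φ((1.96 − 1.342)/0.707) = 81%, against 54% when paired. The choice of an unpaired test is a separate defect and is not counted here.

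**Step 3. What the goal would need if kept.**

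For a one-sample non-inferiority comparison with a fixed standard value (one-sided 0.025, 80% power, true mean equal to the standard), the smallest workable margin is (1.960 + 0.842)/√n = 2.802/√n, in SD of the quantity compared. That is 0.44 SD at n = 40, 0.32 SD at n = 75 and 0.23 SD at n = 150.

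These are normal-theory figures. Both scales are ordinal and bounded, so they are indicative only.

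**The case against.** The strongest defence has four parts.

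1. *No rule equates non-significance with equivalency.* This is correct. A reader might infer that p > 0.05 will count as meeting the goal, but the documents never say how such a result will be interpreted. It is a risk that the plan leaves open.
2. *The pre/post test is not the only analysis, and the cited sources may hold the standard values.* This is also correct as far as it goes. The Chi-square test, the group correlations and the later comparison with existing studies are all mentioned. None has a reference value, margin or decision rule, so none fills the gap. Values that may exist in a cited source are not pre-specified until the protocol names them.
3. *Figures at 40 patients show only the worst case.* Forty is a minimum target, and Study Design plans to recruit as many as possible. At 150 the chance of missing a 0.3 SD decline falls to 5%. That is why a range is given. The missing comparator is unaffected by n.
4. *This is a pilot of acceptability, judged on KPIs.* This limits the consequence. However, the exemption from statistical analysis covers the primary outcomes only; significance testing is planned for these secondary ones.

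A reader might also infer that no change is the expected result, because entry requires patients "to look after own affairs without assistance i.e. a Modified Rankin Scale" of 2 or below. The documents do not support this. The limit applies to Rankin, not Barthel. Patients at grade 1 or 2 can still improve, and recovery is plausible in subacute patients.

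**Conclusion.** The stated secondary goal cannot be reached by the stated analysis, whatever the p-value. That conclusion comes from reading the sections side by side and rests on no numerical assumption.

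The figures show only how little a non-significant result would exclude. A 0.3 SD decline would go undetected in 54% of trials at the minimum target and 5% at the device ceiling; a 0.2 SD decline in 77% and 32%. They depend on assumed effects in SD units, a paired test, a two-sided 5% level and approximate normality.

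The primary KPIs are unaffected, and no decision rule in the documents rests on Barthel or Rankin. The correction should be made because it changes what the secondary results may be said to show.

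**What to change.** **Preferred.** In Study goals and objectives, delete equivalency and the comparison with unnamed standard values. In Data Management and Statistical Analysis, report:

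- the mean within-patient Barthel change with a 95% confidence interval;
- Rankin as numbers improved, unchanged and worsened, with the number already at the best grade at baseline.

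State that a non-significant change will not be described as equivalency.

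**If the goal is kept.** For each scale:

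- name the standard value and its source, and say whether it is an end score or a change;
- fix and justify a one-sided non-inferiority margin beforehand, since improvement also meets the goal;
- claim the goal only if the confidence interval for the difference from that standard value excludes a deficit larger than the margin.

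The margin should not be applied to change from the patient's own baseline. That would show similarity to baseline and repeat the present mismatch. At 40 patients a margin much below 0.44 SD would leave this comparison with less than 80% power.

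**Cost.** Protocol wording only under the preferred option, with no added patients, visits or measurements. The secondary claim becomes more modest. Keeping the goal also requires finding and defending a standard value and margin for each scale.

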The goal of this study is to investigate the applicability and utility of an innovative technology product such as WeReha to the home rehabilitation of stroke patients as an integrative solution to

a conventional exercise program and to assess its acceptance by the patient, caregivers and clinic professionals.

Patients will use WeReha for their home rehabilitation in addition to traditional treatments for up to 12 weeks. The Inclusion criteria for the study have been kept broad in order to assess these factors on a large enough scale, so as not to limit the usage of the device to a specific sub-group of patients. If patients enrolled are in a subacute phase (i.e. within the first 6 months after the stroke onset), they will be enrolled before leaving the hospital or the rehabilitation department and reaching their home. If patients are considered to be in their chronic phase (i.e. over 6 months after stroke onset), they will be enrolled during an outpatient treatment or on a volunteer basis.

Before starting the trial with WeReha, every patient enrolled will receive proper training from a person dedicated to the project (who will be referred to as the “dedicated figure”) appointed by the hospital and financially supported by the sponsor of the study.

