## Methodology

At the trial site, the sponsor of the study will contribute to pay “dedicated figures”, a member of the clinical care team with a specialisation in clinical research (either a nurse or a physiotherapist) selected by the trial site personnel itself, as indicated by the scope of the Magic project [5]. Such figures will be the only people who will have access to all patient clinical records during the whole research study period, including the screening for patients. The dedicated figures will be educated by the sponsor (CoRehab) before starting the study in order to become a WeReha’s expert. They will be instructed on managing technical issues and details regarding the general functioning of the device (how to navigate the device, how to recharge the tablet and the sensor, how to position the sensor inside the objects and how to use them during game, how to wear the sensor) and for additional support they will be provided with a detailed manual for reference. . The sponsor will provide remote support to patients once at home in the first instance using a specific UK telephone number that will be provided to all participants. The WeReha software and manual will also have this phone number. The sponsor will inform the PI of all communication with participants and identify if this was technical (e.g. how to recharge the sensor, what to do if the system seems to be frozen and does not respond, what to do if the sensor does not switch on) or clinical. If it is a clinical difficulty then the PI will make contact with the participant. The dedicated figures will be provide training to patients and caregivers before receiving the device and go home.

Recruitment will start when patients are still in hospital after the onset of their stroke, as early rehabilitation can provide to better results. Whenever a patient is informed about the study or requests information and the inclusion/exclusion criteria are met, the dedicated figure will report that a patient could be enrolled in the study. If a patient accepts to partecipate in the study, he/she have to sign the appropriate documentation within 48 hours.

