Following discharge, participants will be reviewed in their own environment by the PI to ensure that the device is set up appropriately so that they can perform the exercises assigned. Participant usage of the device will be monitored at eight weeks. If at this stage the participant has not had four active weeks then the PI will review the patient with the expectation of the device being returned. In certain cases patients may have been unwell for a prolonged period and unable to use the device and it will be left to the PI to decide whether to remove the device or to allow the patient to continue using it for the full 20 weeks. All participants recruited to the study will be asked to complete the Technology Assessment Model questionnaire. After 20 weeks, the patient will return the WeReha device and the designated person will complete final assessments (clinical evaluation and questionnaires).

Identifiable data will be retained for the whole research study period. The data retention policy is clearly stated in the Patient Information Sheet. Since the Community Stroke Team provides therapy to patients, the team will highlight any capacity/ safety issues at any time and will then manage the patient to ensure safety.

Once the WeReha is returned to the hospital after being used by a patient, the dedicated person will follow a specific procedure in order to make the device available for any future usage by another patient. This procedure consists of resetting data through the specific button in the administration area of the software and cleaning as per infection control procedures for all the

reusable HW components. Also, new single use components (straps and smart objects) will be prepared for a new patient, so that the device is completely reusable.

Throughout the study, WeReha will suggest exercises in different forms to support rehabilitation of the most important body functions.

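### The plan sets out to demonstrate logistical and economic benefits, but it measures only burdens that WeReha adds and has no comparator, cost or saving measure, so no benefit can be shown

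*Combined protocol and SAP*

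**What the plan says.** Study goals and objectives states the aim: "we want to demonstrate the logistical and economic benefits of the deployed solution". The next sentence names two measures: the time taken to train patients and caregivers, and "the number of times patients contact the sponsor for technical assistance".

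Secondary Outcome Measures lists the same pair in slightly different terms:
- "Time dedicated by the specialised personnel to each patient for training to learn the WeReha device before leaving the trial site", in minutes per patient
- "Number of calls per week for clinical and technical assistance specific for the WeReha device", recorded by the sponsor

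Project summary makes the device an add-on: "Patients will use WeReha for their home rehabilitation in addition to traditional treatments".

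Methodology describes PI work that is not part of any outcome:
- After discharge, "participants will be reviewed in their own environment by the PI to ensure that the device is set up appropriately".
- For a participant without four active weeks at week 8, "then the PI will review the patient with the expectation of the device being returned".
- On calls to the support line, "If it is a clinical difficulty then the PI will make contact with the participant".

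Study Design restricts all secondary outcomes to active patients, meaning those with at least four active weeks.

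**The concern.** A benefit is what is saved less what is spent. Both measures lie on the spending side, because a patient without WeReha needs no training on it and makes no calls about it. Nothing in the outcome list lies on the saving side.

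The rationale section justifies the project largely on cost-effectiveness. It says that economic and logistical gains from home technology are generally assumed and have not been studied on a large scale. According to Anticipated Results of the Study, the buyers group will collate the findings. Short training and few calls, reported under an aim to demonstrate benefits, could be taken by that audience as evidence of a saving that was never observed. A time figure that stops when the patient goes home would also leave out device set-up work that the protocol itself plans.

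**Working it through.** The plan states no sample size, target or cost figure for this aim, so there is nothing to reproduce. The check has four steps.

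**1. Can the measures identify a benefit?** Write B = S − A, where S is staff time or cost saved relative to care without the device, and A is what the device adds. Training minutes and calls are both parts of A. No outcome covers therapist time saved, visits avoided, service use, device cost or unit costs, so S is unobserved. If both parts of A came out at zero, B would equal S and would still be unknown. More patients sharpen A and do nothing for S. Calls are a count logged by the sponsor, not minutes, so even A cannot be totalled in one unit.

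**2. Does another section supply a comparator?**

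| Section | What it offers | Does it cover training time or calls? |
|---|---|---|
| Study goals and objectives | Comparison with standard values | No: Barthel and Rankin scores only |
| Data Management and Statistical Analysis | Pre versus post test for secondary outcomes | No: neither measure has a pre value |
| Secondary Outcome Measures | No KPI or threshold for either measure | No |
| Anticipated Results of the Study | Later collation and comparison with existing studies | No: no economic or logistical measure is named |
| Project summary | Device on top of usual treatment | No: no usual service is replaced |

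**3. How much could the home set-up review add?** Methodology expects training to take t = 30 to 60 minutes. The length h of the home review is not given; 15 to 60 minutes is assumed here. Added share = h / t.

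| h (assumed) | t = 30 min | t = 60 min |
|---|---|---|
| 15 min | 15/30 = 50% | 15/60 = 25% |
| 30 min | 30/30 = 100% | 30/60 = 50% |
| 60 min | 60/30 = 200% | 60/60 = 100% |

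At the enrolment KPI of 50, training comes to 50 × 30 to 60 minutes = 25 to 50 hours. The home review would come to 50 × 15 to 60 minutes = 12.5 to 50 hours on the same assumption.

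**4. What does the active-patient rule remove?** At the two KPIs, 50 enrolled and 40 active, (50 − 40)/50 = 20% of trained patients leave the analysis. Their training is 10 × 30 to 60 minutes = 5 to 10 hours. The KPIs are minimum targets, so this illustrates the effect and does not forecast it.

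**The case against.** The strongest reply is that the sentence is an aspiration in a pilot whose stated goals are acceptance and validity. Success is judged on the primary KPIs, and no planned decision rests on an economic result. The outcome list is already descriptive. The training measure is explicitly confined to training on site and measures what it says. This limits the weight of the point, but it does not rescue the aim: the sentence is tied directly to two listed outcomes that cannot deliver it.

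Four stronger readings are tempting, and the documents do not support them.
- *The 8-week PI review is a routine cost per patient.* It applies only to participants without four active weeks at that time. Most of them would fall outside the active-patient set; the exception is those whom the PI allows to continue and who later reach four.
- *Both measures are staff time.* The second is a count of calls and only a proxy for effort.
- *The plan understates total running cost.* It never presents training minutes as a total, and it does not say whether PI reviews would exist in routine use or belong to trial conduct. What can be said is narrower: the home review's stated purpose is device set-up, and its time goes unrecorded.
- *The 25% to 200% range is a measured bias.* It depends wholly on an assumed visit length.

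**Conclusion.** The concern holds. The design can describe part of the workload that WeReha adds, but it cannot show a logistical or economic benefit. That conclusion is logical and needs no assumption. It does not mean that WeReha has no such benefit, and the primary outcomes are unaffected.

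The omission of the home set-up review is also clear from the text. Its size is not: 25% to 200% of training time holds only if the review lasts 15 to 60 minutes, travel excluded, and training lasts the 30 to 60 minutes expected. The 20% loss from the active-patient rule holds if enrolment and activity land exactly on their KPIs and training time is similar in drop-offs.

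**What to change.** 1. In Study goals and objectives, replace the aim of demonstrating benefits with one of describing the staff time and support calls needed per patient.
2. In Secondary Outcome Measures, add the minutes of the PI's home set-up review to the logged personnel time.
3. Report training time, set-up time and calls for all enrolled patients, as a stated exception to the active-patient rule in Study Design, so that effort spent on drop-offs is counted.
4. PI time on the 8-week review can be logged as a separate conditional item, not averaged in as a routine cost per patient.

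This asks for no control arm or health-economic study and leaves patient management unchanged. The cost is a wording change and one more field in the time log, with a further entry if the 8-week time is kept. The claim becomes more modest and the reported staff time higher.
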